Study of APRV and ICP in Patients with Severe Traumatic Brain Injury

NCT 02507973

Date : 3/24/15

Introduction

Management of patients with Traumatic Brain Injury (TBI) emphasizes on prevention of secondary insults such as hypotension and hypoxemia which negatively impact outcomes¹. Both hypotension²⁻⁴ and hypoxemia^{5,6} are not only independent risk factors for increased mortality in patients with TBI, but also lead to increased intracranial pressure (ICP), which is also another independent risk factor for high mortality^{4,7-10}.

All patients with severe TBI (Glasgow Coma Scale ≤ 8) require sedation and mechanical ventilation for airway protection, oxygenation and minimization of obnoxious stimuli which may elevate ICP¹¹. Mechanical ventilation, however, carries risks of increasing intrathoracic pressure, airway pressure (Paw) and may lead to increased ICP^{12,13}.

Airway pressure release ventilation (APRV) is a mode of mechanical ventilation that switches between high (P_{High}) and low (P_{Low}) continuous positive airway pressure while allowing spontaneous breathing at both phases. Alveolar recruitment and oxygenation occur during P_{High} whereas ventilation occurs during brief releases to P_{Low} ^{14,15}. APRV has been used successfully in patients with multisystem trauma¹⁶⁻¹⁹. However literature about APRV and patients with severe TBI has been scant as concern that APRV with high positive airway pressure could result in elevated ICP still exists.

Dart et al¹⁶ showed that APRV could be used to improve oxygenation among multisystem trauma patients with ARDS or acute lung injuries, without affecting airway pressure (Paw). The authors informally mentioned that several patients with TBI in their studies tolerated APRV well without increasing ICP. Nemer et al reported that pressure-controlled recruitment maneuver with peak pressure up to 50 cm H₂O for 2 minutes did not increase ICP in patients with subarachnoid hemorrhage²⁰. A single case report published successful oxygenation of a hypoxemic patient with subarachnoid hemorrhage using APRV without increase of patient's ICP²¹. In addition to improving oxygenation, APRV was also shown to improve cerebral blood flow and spinal blood flow in animals undergoing APRV with spontaneous breathing²².

Hypothesis

Therefore, we hypothesize that APRV could be safely used in patients with severe TBI as it does not increase their ICP and compromising their Cerebral Perfusion Pressure (CPP), while preventing hypoxemia and hypercapnia in these patients.

Project Primary Goal

This pilot study, to the best of our knowledge, is the first study that specifically investigates the efficacy of APRV among patients with severe TBI. We aim to investigate whether APRV can safely oxygenate patients without compromising their ICP and CPP.

Study Personnel

Principal Investigator: [name]

Co-investigator: [name] (point of contact)

Drs. [name], [name], [name], [name], [name], [name], [name], [name], [name].

Study Methodology

Methods:

We will conduct an observational crossover study. We aim to recruit 50 patients with severe TBI requiring intracranial pressure monitoring during their stay at the Neuro Trauma ICU at the R Adams Cowley Shock Trauma Center. Each patient at admission will initially receive a primary mode of mechanical ventilation as determined by the attending trauma intensivists.

12-18 hours after recruitment, continuous monitoring of patients' ICP and hemodynamic status (ICP, HR, RR, SpO₂, EtCO₂, MAP, CPP, SpO₂, and EtCO₂) will commence to collect patients' baseline data for 30 minutes. Patients will then undergo low tidal volume mechanical ventilation (LOTV), serving as a control mode of ventilation, for 2 hours prior to switching back to the primary mode of ventilation for 30 minutes. Next, patients will be placed on APRV for 2 hours. While receiving APRV, patients' ICP and hemodynamic status will be continuously monitored and recorded for comparison and analysis. After 2 hours of APRV, patients will be switched back to their previous mode of ventilation and more data are collected for another 30 minutes. This sequence of ventilation is illustrated in figure 1.

Intracranial pressure will be measured every 15 minutes during the study period. While undergoing low tidal volume ventilation and APRV, patient's volume statuses and cardiac functions will also be assessed using a non-invasive, non-radioactive modality such as Transthoracic Echocardiography.

Figure 1. Sequence of mechanical ventilation and data collection.

[figure not shown]

Figure 2. Flow chart of APRV Protocol:

[figure not shown]
[figure not shown]

Figure 3. Flow Chart for LOTV protocol

Inclusion Criteria

- Intracranial pressure monitoring
- Mechanically ventilated

Exclusion Criteria

- Age < 18
- Pregnant women
- Prisoners
- Initial mode of ventilation = APRV
- Providers' judgments

Consent:

The patients will not be able to consent for themselves, due the severity of their conditions. We will seek consent from legally authorized representative if available or patients' next-of-kin.

Outcomes

- Primary outcome: ICP
- Secondary outcomes: MAP, CPP, SpO₂, EtCO₂, any interventions for ICP or for hemodynamic instability.

Analysis Plan

Data Security:

Patient's data will be recorded on a standardized Microsoft Excel spreadsheet. This spreadsheet will first be password-protected, then encrypted by commercial 128-bit encryption software (www.boxcryptor.com). The encrypted spreadsheet then will be stored in a secure, password-protected online storage with extra security designed for corporation (OneDrive for Business by Microsoft Corporation, Redmond WA; <https://onedrive.live.com/about/en-nz/business/>).

These measures of security allow maximal collaborations between investigators while enhancing safety for patients' protected health information.

Data Analysis:

We aim to report our findings as following:

Table 1. Patient Demographics
Number of patients
Age (years)
Gender
BMI
Mechanism of injury Motor vehicle collision, n (%) Gunshot wound, n (%) Fall, n (%)
GCS score
ISS
Primary mode of mechanical ventilation
PaO ₂ /FiO ₂ ratio
ICU length of stay (days)
Hospital length of stay (days)
Mortality

Table 2. Outcome Measurements						
Dependent Measure (Mean, Interquartile)	Baseline	LOTV	APRV	Conventional MV		p-value
				Pre-APRV	Post-APRV	
ICP						
MAP						
CPP						
CVP						
Heart Rate						
Respiratory Rate						
SpO _p						
EtCO ₂						
Volume status by TTE						
Therapeutic interventions for ICP, blood pressure						

Table 3. Adverse Events	
Patients not tolerating APRV N, (%)	

Causes N, (%)	Elevated ICP
	CPP < 50
	Hypoxemia
	Hypercapnia
	Tachycardia

All continuous variables will be reported as mean with interquartile values (IQR).

Estimated Study Length

There were 1259 patients with isolated blunt TBI (Abbreviated Injury Scale of brain was ≥ 2 while AIS for other body region was ≤ 2) admitted to the R Adams Cowley Shock Trauma Center in 2013. Therefore, we estimate that we will be able to recruit 2-3 patients per week.

Our pilot study is expected to finish recruitment within 6-8 months.

Target Conferences

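### The plan makes a no-increase claim about ICP but sets no acceptable rise and reports only means, IQR and a p-value, so a non-significant result could be read as safety

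*Combined protocol and SAP*

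**What the plan says.** The Hypothesis section proposes that "APRV could be safely used in patients with severe TBI as it does not increase their ICP and compromising their Cerebral Perfusion Pressure (CPP"). The Project Primary Goal puts the same idea as an aim: "We aim to investigate whether APRV can safely oxygenate patients without compromising their ICP and CPP". Neither sentence gives an amount in mmHg. Under Outcomes the endpoint is given only as "Primary outcome: ICP".

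On size, Methods says "We aim to recruit 50 patients with severe TBI requiring intracranial pressure monitoring". No SD, power, alpha or expected precision accompanies the number. The study is described as a pilot ("This pilot study, to the best of our knowledge, is the first study") and as a crossover ("We will conduct an observational crossover study"). Each patient has 2 hours of LOTV, named as the control mode, and later 2 hours of APRV, with ICP read every 15 minutes.

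On analysis, Data Analysis says "All continuous variables will be reported as mean with interquartile values (IQR"). Table 2 has five condition columns (baseline, LOTV, APRV, and conventional ventilation before and after APRV) and a single p-value column, with no test, contrast or level named. Table 3 lists reasons for not tolerating APRV. One has a number (CPP below 50); elevated ICP, in the same list, has none.

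**The concern.** A claim that a treatment does not raise ICP needs a statement of how large a rise would still count as none. It also needs an output showing that larger rises have been excluded. The plan supplies neither for mean ICP. A mean with IQR describes the spread between patients, and a p-value tests whether the difference is zero. Neither shows how large a rise remains compatible with the data.

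Followed as written, the plan leaves non-significance as the only inferential support for the claim. That support is easiest to obtain when the data are noisy, so the error runs towards calling the mode safe. The Introduction treats raised ICP as an independent risk factor for death and says that concern about APRV raising ICP persists. This is the question on which a reader will rely on the study.

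**Working it through.** **1. The plan's own figure.** The target of 50 can be neither reproduced nor refuted, because no alpha, sidedness, power, margin or SD is given. The recruitment text does not derive it either. At 2 to 3 patients per week and 4.345 weeks per month, 6 to 8 months gives 2 × 6 × 4.345 ≈ 52 up to 3 × 8 × 4.345 ≈ 104 patients.

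**2. Inputs.**
- From the documents: n = 50, each patient measured under both LOTV and APRV, so the differences are paired.
- Assumed: all 50 pairs complete; two-sided 0.05 test; a true mean rise of 2 mmHg for illustration; SD of the within-patient difference 5, 8 or 10 mmHg, with 3 mmHg added as a favourable case.

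**3. Chance that a true 2 mmHg rise is non-significant.** SE = SD/√50 and noncentrality = 2/SE. The critical value is t(0.975, 49) = 2.010. The chance of a miss is the probability that a noncentral t with 49 df falls between −2.010 and 2.010.

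| SD (mmHg) | SE | 2/SE | Missed |
|---|---|---|---|
| 3 | 0.424 | 4.71 | 0.4% |
| 5 | 0.707 | 2.83 | 21% |
| 8 | 1.131 | 1.77 | 59% |
| 10 | 1.414 | 1.41 | 72% |

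**4. One dataset, different verdicts.** Take an observed mean rise of 1.5 mmHg with SD 5. The 95% CI is 1.5 ± 2.010 × 0.707 = 0.08 to 2.92, with p = 0.039. A 0.05 test calls this an increase. It passes a margin of 3 mmHg and fails a margin of 2 mmHg. Both margins are illustrations only; the documents give none.

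**5. Precision that 50 patients buy.** The 95% CI half-width is 2.010 × SD/√50 = 0.284 SD. That is 0.85, 1.42, 2.27 and 2.84 mmHg at SD 3, 5, 8 and 10. If only 40 pairs were complete, it would be 2.023 × SD/√40 = 0.320 SD.

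**The case against.** The strongest reply is that this is a pilot with an exploratory aim, and that it is being held to the standard of a confirmatory non-inferiority trial. Much of that stands. A pilot needs neither a power calculation nor a formal justification of 50, and their absence is not the fault here. What remains is that the hypothesis is worded as a no-harm conclusion and p-values are planned for it. The pilot label does not make those outputs able to support that conclusion.

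Three stronger readings are tempting, and the documents do not support them.

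- A reader might infer that the investigators will choose the pass mark after seeing the data, or will treat p > 0.05 as proof of safety. No such rule is written. The text shows only that nothing is fixed beforehand and that this route is open.
- A reader might infer that the plan has no ICP threshold at all. Figures 2 and 3, the APRV and LOTV flow charts, are not shown and may contain per-patient ICP limits. Such limits would define whether a patient tolerates a mode. They would not be a margin on the mean difference, although tolerance counts could inform a judgement of safety.
- A reader might infer that 50 is too few. That depends on an SD and a margin that the documents do not give. At SD 3 a 2 mmHg rise would almost never be missed.

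It is also fair to say that the miss rates reflect assumed SDs. They show what could happen and do not predict this study's results.

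**Conclusion.** The point holds as a mismatch between claim and output. The plan states that APRV does not raise ICP, sets no acceptable rise in mean ICP in its readable text, and plans only descriptive summaries and a p-value. If non-significance were taken as support, a true 2 mmHg rise would go undetected about 21%, 59% or 72% of the time at SD 5, 8 or 10 mmHg. This assumes 50 complete pairs and a two-sided 0.05 test. The mismatch itself does not depend on these figures; its practical size does, and it would be negligible for this rise at SD 3. The wording should be changed before enrolment. The finding does not show that 50 is the wrong number.

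**What to change.** **Preferred, because this is a pilot.** Replace the ICP part of the hypothesis with an estimation aim:

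> To estimate the mean within-patient difference in ICP, APRV minus LOTV, using each patient's mean of the 15-minute readings in each 2-hour period, with its two-sided 95% confidence interval.

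LOTV is used because the plan names it as the control. Add to Data Analysis that a non-significant p-value will not be reported as showing no increase.

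**If the no-increase claim is kept.** Fix a margin D, in mmHg, before enrolment and on clinical grounds alone; its value is for the investigators to set. Claim no increase beyond D only if the upper limit of the two-sided 95% CI for the same difference lies below D. Otherwise report the result as inconclusive. D should not be worked back from the sample size.

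**In either case.** Next to the target of 50, state the expected precision: a half-width of about 0.28 SD with 50 complete pairs, with the assumed SD and its source, and wider if some patients do not tolerate APRV.

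**Cost.** A few sentences in Hypothesis, Methods and Data Analysis. The estimation aim needs no extra patients or measurements. Some results that could now be reported as no increase would become inconclusive. If the investigators choose a strict D, 50 patients may be too few to meet it.

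### EtCO₂ is the only CO₂ measure specified and is compared across LOTV and APRV as one quantity, so on its own it cannot support a claim of preventing hypercapnia

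*Combined protocol and SAP*

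**What the plan says.** The Hypothesis section proposes that APRV can be used safely in severe TBI without raising ICP or compromising CPP, "while preventing hypoxemia and hypercapnia in these patients". Prevention of hypercapnia is therefore part of the stated hypothesis.

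The CO₂ measurements in the readable text are these:

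- **Methods, monitoring list:** "ICP, HR, RR, SpO₂, EtCO₂, MAP, CPP, SpO₂, and EtCO₂) will commence to collect patients' baseline data for 30 minutes". EtCO₂ appears twice and PaCO₂ does not appear.
- **Outcomes:** "Secondary outcomes: MAP, CPP, SpO₂, EtCO₂, any interventions for ICP or for hemodynamic instability".
- **Table 2:** one EtCO₂ row under Baseline, LOTV, APRV and conventional ventilation before and after APRV, with a single p-value column. No test is named.
- **Table 3:** hypercapnia is one of the causes of intolerance of APRV. No measure or threshold is given, and there is no matching count for LOTV.
- **Table 1:** PaO₂/FiO₂ is a single descriptive row, not broken down by mode.

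On the modes themselves, the Methods section says: "Patients will then undergo low tidal volume mechanical ventilation (LOTV), serving as a control mode of ventilation, for 2 hours". During APRV, "patients' ICP and hemodynamic status will be continuously monitored and recorded for comparison and analysis". The Introduction describes APRV as a mode in which "Alveolar recruitment and oxygenation occur during P_{High} whereas ventilation occurs during brief releases to" the low pressure level, "while allowing spontaneous breathing at both phases".

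**The concern.** Hypercapnia is ordinarily a statement about arterial CO₂. EtCO₂ can stand in for it in a between-mode comparison only if the PaCO₂–EtCO₂ gap is the same in each mode. The protocol's own description of APRV gives reason not to take this for granted, because the exhaled breath that the monitor samples is of a different kind. It may be a brief release, or a spontaneous breath at either pressure, where LOTV delivers a conventional tidal breath. A release that ends early, or a small spontaneous breath, could lower EtCO₂ relative to PaCO₂. Better recruitment could narrow the gap instead.

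The crossover does not remove this. It cancels whatever is constant within a patient, but an error that changes with the mode stays in the APRV-minus-LOTV difference.

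What is at stake is the hypercapnia part of the conclusion. Equal or lower EtCO₂ on APRV could be reported as hypercapnia prevented while PaCO₂ was higher. A change in the gap alone could equally appear as a CO₂ difference between modes.

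**Working it through.** There is no figure in the plan to reproduce. The target of 50 patients comes without alpha, power, effect size or SD, and no PaCO₂–EtCO₂ gap is given for either mode. The one input below taken from the documents is n = 50. Everything else is an assumption, used to show scale.

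**Step 1: what the comparison identifies.** In each mode, PaCO₂ = EtCO₂ + gap. Subtracting LOTV from APRV:

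ΔPaCO₂ = ΔEtCO₂ + Δgap.

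Table 2 supplies ΔEtCO₂. Nothing in the readable text supplies Δgap.

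**Step 2: size in mmHg, with EtCO₂ assumed to be 38 in both modes and the LOTV gap assumed to be 5.**

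- LOTV: 38 + 5 = 43.
- APRV, gap 8: 38 + 8 = 46, a rise of 3.
- APRV, gap 12: 38 + 12 = 50, a rise of 7.
- APRV, gap 3: 38 + 3 = 41, a fall of 2.

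Table 2 would show zero difference in all three cases.

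**Step 3: size against sampling error.** Assume a paired comparison of 50 patients, two-sided alpha 0.05, equal true PaCO₂ in both modes, and a gap that differs by δ. Then SE = SD_diff/√50, the 95% half-width is 1.96 × SE, and the chance of p < 0.05 is Φ(δ/SE − 1.96) + Φ(−δ/SE − 1.96).

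| SD_diff (mmHg) | 95% half-width | δ = 1 | δ = 2 | δ = 5 |
|---|---|---|---|---|
| 3 | 0.83 | 0.654 | 0.997 | 1.000 |
| 5 | 1.39 | 0.293 | 0.807 | 1.000 |
| 8 | 2.22 | 0.143 | 0.424 | 0.993 |

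A gap shift of a few mmHg is therefore comparable to or larger than the random error. It can produce a significant EtCO₂ difference with no PaCO₂ difference behind it, and a shift the other way can hide a real one.

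**Step 4: effect on a count of hypercapnia.** Assume PaCO₂ has mean 40 and SD 5, with a line drawn at 45 mmHg purely for illustration. This is not a proposed threshold.

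- True share above the line: 1 − Φ((45 − 40)/5) = 15.9%.
- Share seen by EtCO₂: 1 − Φ((45 − 40 + gap)/5), which is 8.1%, 2.3% and 0.5% for gaps of 2, 5 and 8.

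So a gap common to both modes already changes the count. With identical PaCO₂ distributions but a gap of 2 in one mode and 5 in the other, the counts would read 8.1% against 2.3%.

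**The case against.** The strongest reply has four parts.

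**Hypercapnia may not be judged from EtCO₂ at all.** A reader might infer that EtCO₂ alone decides whether a patient is hypercapnic. The documents do not establish that. The Table 3 event has no stated measure and could be arterial, and the APRV and LOTV flow charts (Figures 2 and 3) could not be read in the copy reviewed and may hold CO₂ criteria. This stands. It does not put PaCO₂ into the listed outcomes or Table 2, however, and Table 3 covers APRV only, so it cannot replace a between-mode comparison.

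**The gap difference is not documented.** The Introduction describes releases and spontaneous breathing. It says nothing about end-tidal sampling, and it also says these patients need sedation, so the amount of spontaneous breathing is unknown. This stands too. It would be wrong to assert that EtCO₂ is biased on APRV, or in which direction. The supportable statement is that equality is assumed without a check.

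**The primary result is untouched.** A reader might infer that an unmeasured CO₂ difference undermines the ICP comparison. It does not. The question is whether the mode raises ICP, and any effect acting through CO₂ is part of the mode's effect. The primary goal names oxygenation, ICP and CPP, not CO₂. The issue would reach ICP only if the report used EtCO₂ to explain an ICP difference or its absence.

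**Scheduled gases would be an added procedure.** The study calls itself observational and has no budget, and PaO₂/FiO₂ in Table 1 does not show that gases fall inside the study windows. This stands, and it is why the fix uses only gases already charted.

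**Conclusion.** The point holds in a limited form. In the readable text, EtCO₂ is the only specified CO₂ measure, it is compared across modes as one quantity, and hypercapnia is undefined. The hypercapnia part of the hypothesis therefore cannot rest on a cross-mode EtCO₂ comparison alone.

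The size is not determined by the documents. The range from 7 mmHg higher to 2 mmHg lower, and the probabilities and percentages above, depend on assumed gaps, SDs and distributions, and even the sign is open. What they show is that a shift of a few mmHg would matter at n = 50.

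This concerns one secondary measure in a pilot study and is a cheap improvement. It does not support the conclusions that EtCO₂ is known to mislead on APRV, or that the ICP comparison is invalid.

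**What to change.** 1. Add a PaCO₂ row to Table 2, abstracted together with the simultaneous EtCO₂ from arterial gases already charted during the Baseline, LOTV and APRV windows.
2. Report the PaCO₂–EtCO₂ gap by mode, and the number of patients with a gas in both LOTV and APRV.
3. Base any statement on hypercapnia on those paired patients. Define the event by the same measure in both modes and give the LOTV count beside the APRV count. The threshold is for the investigators to set. If Figures 2 or 3 already contain a CO₂ criterion, the Table 3 definition should be reconciled with it.
4. If paired gases are too few, limit the study-level conclusion to the EtCO₂ comparison and drop the claim of preventing hypercapnia. This applies to the study's conclusion as a whole and should not be varied by patient.

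The cost is a little more chart abstraction and possibly a narrower claim. No additional blood draws are needed. Because gases are drawn for clinical reasons, the paired patients may be a selected group. Reporting their number lets the reader judge how far the result extends, but does not remove the selection.

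### Table 3 counts intolerance for APRV only, so the APRV figure has no LOTV control and cannot be attributed to APRV

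*Combined protocol and SAP*

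**What the plan says.** Study Methodology describes a fixed sequence in the same patients, with 50 planned. LOTV comes first, "serving as a control mode of ventilation, for 2 hours". After 30 minutes back on the primary mode, "Next, patients will be placed on APRV for 2 hours". Patients then return to the previous mode and "more data are collected for another 30 minutes". ICP is read every 15 minutes.

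The Outcomes section gives "Primary outcome: ICP" and includes among the secondary outcomes "any interventions for ICP or for hemodynamic instability". Table 2 has LOTV and APRV columns, with a row for ICP and a row headed "Therapeutic interventions for ICP, blood pressure".

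Table 3, the adverse-event table, has one intolerance line, "Patients not tolerating APRV N" and percent. Its causes are elevated ICP, CPP below 50, hypoxemia, hypercapnia and tachycardia. It has no line or column for LOTV. The readable text does not say whether ICP readings after an intervention or an early stop stay in the ICP row of Table 2. The APRV and LOTV flow charts (Figures 2 and 3) are not shown.

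**The concern.** The hypothesis is a safety claim: APRV does not raise ICP, and it avoids hypoxemia and hypercapnia. Severely brain-injured patients may have ICP, CPP or oxygenation events during any 2-hour period. Only the excess over the control period speaks to APRV, and Table 3 cannot show an excess. This can mislead either way. A moderate APRV count may look like harm when LOTV is no better tolerated, or be put down to the underlying illness when LOTV was tolerated by everyone.

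The count also bears on the primary outcome. Elevated ICP is a reason for not tolerating APRV, so a rise in ICP can bring about the event that changes or ends the later ICP readings. A flat mean could reflect no rise, or a rise that was treated or cut off. Event counts on both modes help to separate the two.

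**Working it through.** The documents state no event rate, ICP rise or SD, so there is no figure of the plan's to reproduce. From the documents: 50 patients, 2 hours per mode, ICP every 15 minutes (120/15 = 8 readings per mode). All event counts, ICP rises and SDs below are assumptions.

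**1. What a one-sided count can tell.** Take 10 of 50 patients not tolerating APRV (20%) and vary the LOTV count. Newcombe's paired interval uses the Wilson limits (l, u) of each proportion and the correlation φ between the two events:

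lower = d − √[(p₁−l₁)² − 2φ(p₁−l₁)(u₂−p₂) + (u₂−p₂)²]

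upper = d + √[(u₁−p₁)² − 2φ(u₁−p₁)(p₂−l₂) + (p₂−l₂)²]

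Wilson limits: 10/50, 0.1124 to 0.3304; 5/50, 0.0435 to 0.2136; 0/50, 0 to 0.0713. With events independent between modes, φ = 0.

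| LOTV events | Both / APRV only / LOTV only / neither | Table 3 shows | Paired difference (95% CI) |
|---|---|---|---|
| 0 | 0 / 10 / 0 / 40 | 20% | +20.0 points (8.7 to 33.0) |
| 5 | 1 / 9 / 4 / 36 | 20% | +10.0 points (-4.3 to 24.2) |
| 10 | 2 / 8 / 8 / 32 | 20% | 0 points (-15.7 to 15.7) |

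For the middle row: 0.10 − √(0.0876² + 0.1136²) = -0.043 and 0.10 + √(0.1304² + 0.0565²) = 0.242. If the same patients tend to have events on both modes, φ is positive and the interval narrows. Table 3 reads the same in all three rows.

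**2. What ICP-driven events can do to mean ICP.** Assume 20% of patients have an event on APRV, their untreated ICP rise averages 10 mmHg over the 8 readings, and the others have none. The untreated group rise is 0.20 × 10 = 2.00 mmHg. The reported rise (mmHg) under four ways of handling readings is:

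| Shape of rise | Event after reading | All kept, rise fully removed by the event | Cut at event, mean per patient | Cut at event, readings pooled | Event patients excluded |
|---|---|---|---|---|---|
| Sustained | 2 | 0.50 | 2.00 | 0.59 | 0 |
| Sustained | 4 | 1.00 | 2.00 | 1.11 | 0 |
| Steadily increasing | 2 | 0.17 | 0.67 | 0.20 | 0 |
| Steadily increasing | 4 | 0.56 | 1.11 | 0.62 | 0 |
| Transient | 2 | 0.50 | 2.00 | 0.59 | 0 |
| Transient | 4 | 1.45 | 2.90 | 1.61 | 0 |

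Example, transient rise with readings 5, 15, 20, 18, 12, 6, 3, 1 (mean 80/8 = 10) and an event after reading 4. Cut at the event: 58/4 = 14.5, times 0.20 = 2.90. All kept: 58/8 = 7.25, times 0.20 = 1.45. The same patients thus give an overstatement or an understatement, depending on the rule.

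**3. The contrast with LOTV.** With a sustained rise, an event after reading 2, full removal and all readings kept, each event patient shows 10 × 2/8 = 2.5 instead of 10 mmHg:
- 20% v 10% of patients: 0.10 × 2.5 = 0.25 instead of 1.00 mmHg.
- 20% v 20%: 0 instead of 0.
- 10% v 20%: -0.25 instead of -1.00 mmHg.

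The sign of any net bias follows the difference in event rates, which Table 3 does not supply for intolerance.

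**4. Scale.** For an assumed SD of paired differences of 4 to 8 mmHg, the 95% CI half-width is t(0.975, 49) × SD/√50 = 1.14 to 2.27 mmHg. Most of the group-level shifts in steps 2 and 3 lie below the upper end of that range, and many below the lower end.

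**The case against.** The strongest reply is that the plan already compares what matters. Interventions for ICP or hemodynamic instability are a secondary outcome in every mode, and Table 2 has both LOTV and APRV columns for them. That stands, so a reader who inferred that the plan has no control for interventions would be wrong. It does not cover intolerance, which appears in Table 3 alone. The mix of 30-minute and 2-hour columns in Table 2 does not change this: at equal hourly rates a 2-hour column collects four times as many interventions, but LOTV and APRV both last 2 hours.

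A reader might also infer that mean ICP will understate a rise. The documents do not support that. Step 2 of the working shows that readings cut at the event can be unbiased or overstate a transient rise. Stops for hypoxemia, hypercapnia or tachycardia, and blood-pressure interventions, have no fixed direction for ICP.

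A reader might further infer that stopping rules are absent. Figures 2 and 3 are not shown and may define intolerance or stopping for both modes, so no claim is made about stopping rules or care. Finally, the tables are reporting shells, and an unstated rule for later readings is, taken alone, missing detail. It matters here because one of the events that can alter those readings is counted on one mode only.

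**Conclusion.** The point holds for the intolerance count. Table 3 yields a safety figure without a comparator, although the control period has the same length and involves the same patients. In the assumed example, one reported 20% is compatible with a paired difference anywhere from 0 to +20 points.

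For the primary outcome the conclusion is conditional. If ICP-driven treatment or stopping is more frequent on APRV, mean ICP can understate a rise; if it is equally frequent and similar in effect, the net bias is about zero; if it is more frequent on LOTV, the bias reverses. The size is unknown, and the illustrated shifts are often within the likely CI half-width. This affects how the result is interpreted and does not show that it would be wrong. The change is cheap and should be made.

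**What to change.** Recording and analysis only; care is unchanged.

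1. Add an LOTV column to Table 3. Record intolerance or early termination and the same five causes, with the same definitions as for APRV.
2. Report the paired APRV minus LOTV difference in patients with early termination, and separately in patients with any ICP-directed intervention. Give 95% CIs among patients who started both modes, and list those who started only LOTV.
3. Compare ICP between modes in all patients who started both. As the primary handling, use readings on the assigned mode up to any early stop, summarised per patient before averaging. As a sensitivity analysis, include all available readings of the scheduled 2-hour window. Flag those taken after a switch as off-mode, and do not also count them in the Post-APRV column.
4. Interpret the no-increase hypothesis from mean ICP and the paired event differences together. Neither ICP analysis removes the effect of treatment given while the patient stays on the mode.

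The cost is one new LOTV data item (unless Figure 3 already provides for it) and time-stamps for interventions. Limits to state in the report: event decisions are made with the mode known, and the Introduction records existing concern about APRV and ICP. The order is fixed, LOTV then APRV, so time and carry-over effects enter the difference. With 50 patients the CI on the event difference will be wide.
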